### 9.12 Description of Medical Devices (for intraductal fulvestrant use only)

#### 9.12.1 Name of Medical Devices

The FullCYTE® Breast Aspirator and either:

- Jabczenski Ductogram Cannula – G04303 –or most current item number (Cook Medical); or
- IntrocanSafety IV Catheter 24G x 0.55 FEP, Winged, Notched (B Braun)
- An alternative catheter may be used to facilitate drug delivery.

#### 9.12.2 Indications for Use of the Medical Devices

The FullCYTE Breast Aspirator device may be used to identify ductal orifices for subsequent cannulation with the FullCYTE Breast MicroCatheter.

The Site may also use a Jabczenski Ductogram Cannula Microcatheter, the Intracan Safety Catheter or another analogous device that facilitates drug instillation into the milk ducts.

Detailed instructions for intraductal fulvestrant administration and use of devices is located in the administration manual.

### 9.12.3 Description of the Investigational Medical Device

The FullCYTE Breast Aspirator is supplied and manufactured by Atossa Genetics, Inc., using Good Manufacturing Practices (GMP) and following all regulations. Sterile microcatheters sufficient to intraductally instill fulvestrant will be obtained from acceptable suppliers. Preferred devices include the:

- Jabczenski Ductogram Cannula – G04303 –or most current item number (Cook Medical)
- IntrocanSafety IV Catheter 24G x 0.55 FEP, Winged, Notched (B Braun).

**The FullCYTE Breast Aspirator (F-450-02)** device is similar to non-powered breast pumps used to express milk from lactating women. The device is comprised of a rigid polycarbonate cup with an adhesive foam liner used to secure placement around the breast nipple. The polycarbonate cup is attached to a user supplied standard syringe, which is used to pull a gentle vacuum to express breast ductal fluid. The FullCYTE Breast Aspirator device is provided non-sterile and is intended for single patient use only. The Breast Aspirator is packaged in a sealed bag.

[figure not shown]

FullCYTE Breast Aspirator

### 9.13 MicroCatheters

#### Jabczenski Ductogram Cannula

Introcan Safety Catheter 24G x 0.55 FEP, Winged, Notched

Refer to the information provided by the manufacturer.

### **9.13.1 Storage and Handling and Stability**

Store in a cool dry place. See the The FullCYTE Breast Aspirator and microcatheters have expiration dates provided on the device labels.

### **9.13.2 Device Dispensing**

Fulvestrant will be infused in up to five breast ducts. A minimum of five catheters should be dispensed for each subject receiving intraductal fulvestrant administration.

### **9.12.3 Description of Investigational Product**

Fulvestrant will be procured by the hospital pharmacy. The full prescribing information is provided in Appendix 20.3 and can be found at:

<http://www.azpicentral.com/faslodex/faslodex.pdf#page=1>

## **10.0 ASSESSMENT OF EFFICACY**

While the primary objective of this study is safety and tolerability, efficacy parameters are Ki67 ER/PgR expression and tumor size by digital imagery, preferably by mammography.

### **10.1 Pathological Assessment**

The clinic pathologist will conduct the pathologic examinations per institutional standards. Additional instructions are provided by the Sponsor.

The purpose of pathological examination is to provide objective assessment of local effect of fulvestrant on nipple skin, ductal cells (benign and malignant), and surrounding fibroadipose tissues. Specifically, the effect of fulvestrant on cell death (apoptosis and necrosis), proliferation (mitosis), and inflammatory reaction will be examined.

Mastectomy or lumpectomy specimens will be received and processed at the site's laboratory after intramuscular or intraductal therapy per institutional standards. Additional instructions are provided by the Sponsor, to include examination of the tissue for pathological evidence of response. Specific attention will be paid to identify the cannulated ducts. Aided by the colored Hydrogel of mastectomy specimens, the ducts identified in the breast parenchyma will be correlated with duct openings identified on the nipple (with suture), and compare the cannulated ducts (areas) with non- cannulated ducts (areas) for cell death, proliferation, and inflammatory response, as examined using routine hematoxylin and eosin (HE) sections. It is assumed that in most subjects, not every duct will be identified or accessed and in these cases those ducts which are not cannulated will be compared to the ones that were cannulated from a histological stand point. Samples will be stored per site's standard procedures.

A mastectomy or lumpectomy specimen will be dissected and samples taken to measure tissue fulvestrant levels.

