### **5.1 Intraductal Doses of Cytotoxic versus Endocrine Agents**

Most cytotoxic agents are given based upon BSA, whereas endocrine agents such as fulvestrant or tamoxifen are not.

Consequently, the dose used in this study will not be tailored to BSA or body weight. The maximum dose of 500 mg selected for the study is based on US labeled Intra-Muscular (IM) dose. Since milk ducts differ in size and volume, it may not be possible to administer 500 mg (10 mL) in all subjects.

It is possible, but unlikely, that peak plasma concentrations of a dose given intraductally will reach the same level as the same dose given intramuscularly (IM). This is because the agent must diffuse out of the ducts to reach the bloodstream. Eventually the entire dose will be taken up systemically but it will happen over a longer period of time (the peak plasma concentration will be lower but the area under curve [AUC] should be the same). Hence it was decided that the total amount of drug given in a single intraductal installation would not be higher than the typical IM dose of fulvestrant. There will be 5 groups, each consisting of 6 subjects. The first subject of each group will receive fulvestrant administered intramuscularly and the next 5 subjects will receive fulvestrant intraductally.

A maximum of two 5 mL vials, each containing 250 mg fulvestrant may be delivered into one duct or distributed among up to five ducts targeted for intraductal instillation. Ductal systems range in shape, size and volume just as breasts range in shape and size. As noted before, there are a range of ducts (from 5-9) and each duct within a breast is a different size. The ductal systems have the capacity to accommodate a significant amount of fluid. In a breast feeding woman, a single breast can accommodate anywhere from 47.2 mL to 62.8 mL. In a non-lactating woman, it is estimated that each breast duct can be distended with as little as 1 mL and may accommodate up to 20 mL without perforation and only mild discomfort. Based on prior experience with intraductal therapy it was determined that no

single breast would be administered > 10 mL of fulvestrant, to be divided among up to 5 ducts targeted for instillation. This amount, in a non-lactating subject, would limit the risk of perforation and discomfort associated with intraductal instillation.

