## **7.0 TRIAL DESIGN**

This is an open-label, non-randomized pharmacokinetic study of pre-surgical fulvestrant in women scheduled for mastectomy or lumpectomy. Eligible subjects will be identified upon admission to the institution for surgical management of breast cancer or DCIS, specifically mastectomy or lumpectomy. There will be 5 groups, each consisting of 6 subjects. The first subject of each group will receive fulvestrant administered intramuscularly and the next 5 subjects will receive fulvestrant intraductally. Subjects where at least 1 suitable duct is identified may undergo nipple aspiration in order to facilitate duct identification and

intraductal infusion of a fulvestrant accompanied by imaging (saline+ ultrasound). A maximum of 5 ducts will receive intraductal infusion of fulvestrant. Across all ducts, the total dose will not exceed 500 mg (10 mL). All subjects will be monitored for systemic and local adverse events during the procedure, immediately following the procedure, within 30 minutes, 1 hour, 4 hours and by phone following discharge on Days +1 and +2, +7, and pre-operative. Subsequent to mastectomy or lumpectomy, subjects will be assessed for systemic adverse events until discharge. Per schedule specified in Table 1, subjects will undergo serial blood draws to determine fulvestrant blood concentration levels.

When fulvestrant is administered at or below the dose level of 500 mg currently in routine clinical use, emergence of Dose Limiting Toxicities (DLT) is unlikely, but not impossible.

Since only a single instillation of fulvestrant is given in this protocol, dose reduction in individual subjects is not possible. However, if any of the DLT parameters reaches any of the thresholds values set in Section 10.3 the dose in subsequent subjects will be reduced to 250 mg (one 5 mL vial).

The purpose of this observational study is to understand the safety and tolerability of giving the anti-estrogen drug fulvestrant directly into the milk ducts of the breast, and collect any evidence of pathologic response. This study will be conducted under good clinical practice (GCP) guidelines as outlined in Section 15.5 Good Clinical Practice. This will be a single-dose study with two treatment groups: 500 mg administered intramuscularly (n=6) and up to 500 mg administered intraductally (n=24).

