#### 9.3.2 Intraductal Administration of Fulvestrant

The second through sixth (2nd through 6th) subject of each of 5 groups will receive intraductally administered fulvestrant Jabczenski Ductogram Cannula Microcatheter, the IntrocanSafety IV Catheter or other catheter suitable to delivery fulvestrant to the milk ducts. Fulvestrant will be infused in up to 5 breast ducts of the breast containing DCIS or invasive cancer. Ducts infused with fulvestrant will be marked with sutures. If sutures cannot be maintained until mastectomy or lumpectomy, other methods should be employed to mark the ducts, as specified in the instruction manual. At least one photograph of the breast documenting infusion location should be taken for the CRF. Do not instill more than 10 mL (500 mg) (i.e., the maximum delivered dose is never to exceed the dose currently in routine clinical use for intramuscular delivery). Detailed instructions for intraductal fulvestrant

administration and use of devices are located in the administration manual provided and will be performed on the intraductal fulvestrant subjects only.

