#### **9.7 Day of Surgery (DOS) Day 14 to 45**

No study related procedures will take place during surgery. The surgeon will make every effort to maintain the bio-occlusive dressing and nipple markers in the mastectomy specimen unless surgical approach would be compromised. These markers are critical for pathological handling and processing of the mastectomy specimen to determine any effect of drug on treated and untreated ducts.

Upon complete removal of the mastectomy specimen, colored hydrogels (approximately 1 to 2ccs) will be injected into the previously treated ducts to allowed focused pathology assessment. It will then be sent to pathology for histological examination and tissue sample collection. Information regarding pathological assessment is in Section 10.1, Histological Assessment. For lumpectomy, this will not be feasible.

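### The cannulated versus non-cannulated duct comparison does not isolate a fulvestrant effect, because no duct receives the instillation procedure without the drug

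*Combined protocol and SAP*

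**What the plan says.** Section 10.1 says the pathological examination is meant to "provide objective assessment of local effect of fulvestrant on nipple skin, ductal cells (benign and malignant), and surrounding fibroadipose tissues". It adds that "the effect of fulvestrant on cell death (apoptosis and necrosis), proliferation (mitosis), and inflammatory reaction will be examined". The only duct-level method it describes is to "compare the cannulated ducts (areas) with non- cannulated ducts (areas) for cell death, proliferation, and inflammatory response" on routine stained sections of the same breast.

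Section 9.7 repeats the attribution: the nipple markers are to be kept in the mastectomy specimen "to determine any effect of drug on treated and untreated ducts".

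Section 9.3.2 defines which ducts are treated: "Fulvestrant will be infused in up to 5 breast ducts of the breast containing DCIS or invasive cancer". It continues: "Ducts infused with fulvestrant will be marked with sutures". If sutures cannot be maintained, another marking method is used. Section 7.0 adds that saline and ultrasound imaging accompany the infusion.

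**The concern.** A within-breast comparison looks well controlled, since each woman serves as her own reference. It is controlled for the woman but not for what is done to the duct. Inflammation or cell death seen around cannulated ducts could come from the drug, or from cannulating, distending and marking the duct. Sections 10.1 and 9.7 name only the drug.

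Section 13.2 makes signs of topical irritation on the excised specimen part of the primary safety and tolerability endpoint. The synopsis says the study is to inform future studies of this route. If mechanical injury is reported as a fulvestrant effect, or a drug effect is dismissed as mechanical, that later work starts from the wrong premise.

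**Working it through.** **Figures in the plan.** None is given for the duct comparison. The only sample-size figures (Section 13.2: detectable effect sizes of 0.60 and 0.69 with 24 subjects) concern the Ki67 change from biopsy to surgery. Taking a two-sided 5% level, which 13.2 does not state, an exact paired t-test calculation gives 0.597 at 80% power and 0.691 at 90% power, so those figures reproduce. They do not depend on the duct comparison. What follows is a comparison of sections, not a calculation.

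**What each kind of tissue receives under the plan**

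| | Systemic drug | Drug placed in the duct | Catheter, distension, saline imaging | Marker at the nipple opening |
|---|---|---|---|---|
| Cannulated duct, intraductal subject | yes | yes | yes | yes |
| Non-cannulated duct, same breast | yes, to the extent absorbed by surgery | no | no | no |
| Duct in an intramuscular (IM) subject | yes | no | no | no |

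The rows follow from 7.0, 9.3.1, 9.3.2 and 5.1. No row has the procedure without drug in the duct.

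**What the difference contains.** Assume effects add. Let S be the effect of systemic drug, D the local effect of drug in the duct, and P the effect of the procedure and marker.

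- Cannulated duct: S + D + P
- Non-cannulated duct, same subject: S
- Difference: (S + D + P) − S = D + P

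This is one observed quantity with two unknowns. If D = 0, the whole difference is P. If P = 0, the whole difference is D. When both act in the same direction, the procedure's share can lie anywhere from 0% to 100%. When they act in opposite directions, they can partly cancel. Nothing in the documents narrows this.

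**Whether the IM specimens help.** A duct in an IM subject shows S under IM dosing, written S(IM). The contrast with a cannulated duct is (S + D + P) − S(IM) = D + P + [S − S(IM)]. D and P still appear only as a sum. Separating them would need a duct showing S + P.

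**Whether P could matter.** The protocol gives grounds to think so:

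- Section 11.2.1 lists duct injury, bleeding, infection and breast inflammation as added risks of the intraductal process, and names catheter placement as a step in it.
- Section 4.0 reports suspected duct perforation in an earlier intraductal study of cytotoxic agents.
- Sections 9.3.2 and 9.7 intend the markers to stay in place until surgery on Day 14 to 45. They sit at the nipple, and 10.1 names nipple skin as a target tissue.

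The link to inflammation is thus in the protocol's own text. The link to cell death is an inference from duct injury. For proliferation the documents give no specific reason to expect a procedure effect, so the point is weaker there.

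**Selection of ducts.** Treated ducts are those that can be accessed (9.1, 10.1), not a random choice, so accessible and inaccessible ducts may also differ before treatment.

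**The case against.** - **The aim is the route, not the molecule.** The primary objective is the safety and tolerability of giving fulvestrant into the ducts. For that, drug and procedure together are the relevant exposure. This stands, and it is why restating the contrast is enough. It does not rescue wording that assigns the findings to fulvestrant.
- **Section 10.1 states a purpose, with no test or decision rule.** True. The comparison is also absent from the efficacy parameters in 10.0, from secondary objective (a) and from Section 13. This lowers the stakes considerably.
- **Details may sit elsewhere.** The sponsor's additional pathology instructions and the planned separate SAP are not available here. They may cover scoring, but they cannot create a procedure-only duct.
- **IM specimens are already examined and compared.** Section 10.1 covers specimens from both routes, and 13.2 plans a qualitative comparison of the two groups. Only a duct-level read of the IM tissue is unstated, and it could not separate drug from procedure.

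Two stronger readings are tempting and are not supported. A reader might infer that the contrast contains no drug effect at all. It does contain the local drug effect, mixed with the procedure.

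A reader might also infer from "Eventually the entire dose will be taken up systemically" that systemic exposure of the comparator ducts biases the comparison. For a local effect it does not, because the systemic part is common to both sets of ducts and cancels. Section 9.7 itself allows for an effect on untreated ducts. Section 5.1 describes slow uptake, and 13.3 accepts that surgery may precede the plasma peak, so the extent of exposure at surgery is not given. Plasma and tissue levels are measured and bear on that question.

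**Conclusion.** The concern holds in a limited form. As written, 10.1 and 9.7 claim more than the comparison can deliver. It estimates the local effect of drug and procedure together, and it cannot assign inflammation, cell death or nipple-skin changes to fulvestrant alone. The size of the procedure component is unknown and cannot be estimated from the planned data.

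This rests on three premises: infused ducts alone receive catheter, distension and marker; no duct is planned to have the procedure without drug; and the procedure can itself injure or inflame tissue, as 11.2.1 states. The additive notation is only for exposition; without additivity, separating the two is no easier.

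The practical consequence is confined to how the histology, and irritation on the specimen in particular, may be described. The Ki67 analysis and its sample size are unaffected.

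**What to change.** 1. In 10.1 and 9.7, describe the contrast as the local effect of intraductal fulvestrant including the instillation procedure, relative to ducts with at most systemic exposure.
2. State in 10.1 that inflammation, cell death or nipple-skin changes in cannulated ducts cannot be assigned to fulvestrant alone, and carry that statement into the reporting of irritation on the excised specimen.
3. Have the pathologist record changes at suture or other marker sites separately from changes along the duct.
4. Optionally, read the same features on ducts in the IM specimens as a descriptive reference for systemic exposure without the procedure, stating that this does not separate drug from procedure.

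Items 1 to 3 change wording in the protocol and pathology instructions and add one recording item. Item 4 adds a read on tissue already collected: six specimens by the count in 13.2, or five by the group structure in 7.0 (5 groups × 1 IM subject). No new arm, visit or tissue is needed. The downside is a narrower claim about the drug.

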### **10.2 Plasma Drug Concentration Levels**

Subjects will have blood drawn several times (see Table 1) to determine plasma concentration levels pre- and post-fulvestrant administration. The blood processing procedure is provided in the lab manual.

#### **10.2.1 Fulvestrant PK Analysis**

Plasma and tissue concentrations will be determined per the described methodology in the PK report and referencing prior publications.

### 10.3 Dose Limiting Toxicity

If Dose Limiting Toxicities (DLT) are identified meeting the definition set forth below, the dose in subsequent subjects will be lowered to no more than 250 mg total (5 mL). DLT will include any study-drug related grade 5 toxicity (death). In addition, if 20% or more ( $\geq 6$  subjects) exhibit a single study drug-related Grade 3 or 4 adverse event (AE) per the CTCAE or SAE as defined in Section 11.2.3, the dose in subsequent subjects will be reduced to 250 mg. SAE Definition in the following categories: blood/bone marrow, cardiac, general constitutional symptoms, dermatology/skin, gastrointestinal, thrombo-embolic, hemorrhage/bleeding, infection, metabolic/laboratory, musculoskeletal/soft tissue, neurology, pain, pulmonary, upper respiratory, renal/genitourinary, or vascular this will be considered DLT and the study drug dose lowered for subsequent subjects. Additionally, if 50% or more subjects ( $\geq 15$  subjects), experience greater than 5 study related Grade 2 AE, this will be considered DLT and the study drug dose in subsequent subjects be lowered to 250 mg. Subjects who experience an allergic reaction, including anaphylaxis, to the dyes or drugs in this study will not be considered a DLT.

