#### **8.4 Subject Discontinuation**

All subjects have the right to terminate participation in the study at any time. The Investigator also has the right to discontinue the subject's participation at any time

regardless of whether the subject wishes to continue in the study. The Sponsor may discontinue the study at anytime.

In addition, subjects may be withdrawn from the study for the following reasons:

- Occurrence of a clinically unacceptable AE
- Violation of the study protocol or lack of compliance with protocol regimens
- Subject declines further study participation
- Subject withdraws informed consent
- Investigator judges it is in the best interest of the subject

If a subject is withdrawn or discontinues study participation, reasonable efforts will be made to bring the subject in to complete the final study procedures. The subject will continue to be followed and medically managed in accordance with the arrangement that was in place prior to study enrollment. The reason(s) for a subject's discontinuation from the study are to be recorded in the source documentation and on the CRFs.

Any subject, who voluntarily or involuntarily withdraws from the study prior to mastectomy or lumpectomy, will be replaced.

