### 9.11 Pain Assessment

Obtain Pain Assessment (see Appendix B), minimally, according to the following schedule

Visit	Collection Time
Day of Fulvestrant Administration (Day 0)	
 
• Prior to fulvestrant administration and prior to nipple preparation for intraductal subjects
 
• Post Nipple Anesthetic (Intraductal Subjects Only)
 
• At completion of fulvestrant administration/instillation
 
• 30 minutes post administration
 
• 1 hour post administration
 
• 4.5 hours post administration
 

Day +7±2	Any time during visit
Pre-Operative (Day 14 ± 7)	Any time during visit

If, during intraductal fulvestrant infusion, the subject reports Grade 3 or 4 pain (CTCAE criteria) in the breast which does not resolve within 10 minutes after infusion of the drug, treatment of additional ducts will be discontinued. Blood draws and follow-up assessment as well as pathological assessment as described in Section 10.1 will be performed per the protocol.

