**11.2.6 Procedures for Adverse Event Reporting**

An adverse event that fulfills any one or more of the criteria in Section 11.2.5 SAE Definition must be reported as an SAE according to the following guidelines:

The investigator must inform the Atossa medical monitor within 24 hours of learning of event by telephone, text or fax of any SAE which occurs during the course of each subject's study participation (e.g., from enrollment through study termination), whether or not considered causally related to the study procedure.

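### After a study-drug-related death, Section 10.3 only lowers the dose for later subjects: it requires no hold on dosing, and once 250 mg is in force it prescribes nothing new

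*Combined protocol and SAP*

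**What the plan says.** Section 10.3 opens with the consequence of a dose-limiting toxicity (DLT): "the dose in subsequent subjects will be lowered to no more than 250 mg total (5 mL". It then says what counts, beginning with the gravest case: "DLT will include any study-drug related grade 5 toxicity (death". Two further clauses, set at 20% and 50% of subjects, lead to the same cut. Section 7.0 states the response again: "the dose in subsequent subjects will be reduced to 250 mg (one 5 mL vial". Neither section mentions a pause, a review before the next subject, or a step below 250 mg.

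Other sections bear on what would happen after a death:

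- Section 11.2.2 obliges the investigator to judge the intensity of each adverse event and its relationship to study product. Section 11.2.4 gives the scale.
- Section 11.2.6 requires every SAE to reach the "medical monitor within 24 hours of learning of event", whatever its cause, and makes the investigator tell the IRB of unanticipated problems.
- Section 8.4: "The Sponsor may discontinue the study at anytime". Section 15.3 lets the sponsor stop at once when safety is the reason, and 15.4 covers closing a site.
- Section 15.6 lets a change that removes an immediate hazard precede IRB approval, and 16.0 recognises that the IRB may withdraw approval.
- Section 9.11 has one automatic stop, for severe breast pain during infusion: "treatment of additional ducts will be discontinued". It applies within a single subject.

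**The concern.** Safety and tolerability of intraductal delivery is the primary objective (Section 6.1). Section 5.3 presents the trial as a first step for this route, and 11.2.1 says that known fulvestrant side effects may differ in severity or frequency when the drug goes into the breast. The subjects have stage 1 or 2 cancer or DCIS and are awaiting planned surgery.

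In that setting, the response to a death attributed to the drug should stop dosing until someone has decided whether to go on. Section 10.3 does set a response in advance, but it presupposes that dosing continues at a lower dose. A site that followed it to the letter could give the next subject 250 mg before any such decision. If the death occurred at 250 mg, following the section to the letter would change nothing. What is at stake is the exposure of the next subject or subjects while the cause is still unclear.

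**Working it through.** **1. What each provision requires after a related death**

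| Provision | Mandatory? | Tied to dosing the next subject? |
|---|---|---|
| 10.3 and 7.0, cut to 250 mg | Yes | Yes, but it sets the dose and does not hold dosing |
| 11.2.2 and 11.2.4, causality assessment | Yes | No |
| 11.2.6, 24-hour report to the medical monitor | Yes | No |
| 11.2.6 and 16.0, notice to the IRB of unanticipated problems | Yes | No |
| 8.4, 15.3, 15.4, sponsor stops the study or site | No, discretionary | Only if the sponsor acts |
| 15.6, immediate-hazard change | No, permissive | Only if someone acts |
| 16.0, IRB withdraws approval | No, discretionary | Only if the IRB acts |
| 9.11, pain rule | Yes | No, same subject only |

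Only the first row is both mandatory and linked to dosing, and it points to continuing.

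**2. The rule applied to two cases**

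- *Related death at 500 mg.* The DLT definition is met. Later subjects receive no more than 250 mg. Nothing has to happen before the next dose.
- *Related death with 250 mg already in force.* The definition is met again, because 10.3 does not limit it by dose. The response is a dose of no more than 250 mg, which already applies. That wording allows a lower dose, but no lower level is named.

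**3. How often this could matter**

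The plan gives no figure for this clause; one death is enough to meet it. The number of subjects is 30 (Section 13.2). The same base underlies the counts in the other two clauses of 10.3: 0.20 × 30 = 6 and 0.50 × 30 = 15.

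Let d be the per-subject risk of a study-drug-related death. The documents give no value, so 0.1%, 0.5% and 1% are assumptions. A hold can protect someone only if the death occurs among the first 29 subjects:

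P(at least one related death in 29) = 1 − (1 − d)^29

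- d = 0.001: 1 − 0.971 = 0.03
- d = 0.005: 1 − 0.865 = 0.14 (0.135 to three places)
- d = 0.01: 1 − 0.747 = 0.25

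For a second related death, after a first has already brought in 250 mg:

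P(at least two in 30) = 1 − (1 − d)^30 − 30d(1 − d)^29

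- d = 0.001: 1 − 0.97043 − 0.02914 = 0.0004
- d = 0.005: 1 − 0.8604 − 0.1297 = 0.010
- d = 0.01: 1 − 0.7397 − 0.2242 = 0.036

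Both calculations assume independent subjects, one risk for both routes, exactly 30 subjects dosed, and deaths known before the next dose. The second also assumes that the lower dose brings no benefit and that nobody intervenes after the first death.

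**The case against.** The strongest reply is that 10.3 is a dose rule and that stopping belongs elsewhere. Section 15.3 names unacceptable risk as a ground and allows immediate discontinuation; 8.4 and 15.4 add to it. The study is open-label at one site, the investigator must assess causality, and the medical monitor hears of any SAE within a day. After a drug-related death the sponsor, the investigator or the IRB would very probably act. All of this stands. A reader might infer from the concern that the trial cannot be stopped, or that a death would go unreviewed; the documents support neither. What is missing is narrower: a link from that review to dosing, and a pause while the decision is made. Nor does 10.3 switch itself off after the cut. It can be met again, but meeting it again changes nothing.

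The second reply is that the event is remote. It is a single dose capped at the labelled amount, and 7.0 calls DLT at or below that dose unlikely, though not impossible. Section 11.2.1 lists adverse-reaction rates for intramuscular use, the highest being nausea at 14%, but they are ungraded and none is a death rate. Nothing in the documents supports a risk as high as 0.5% or 1%, so the upper two figures only illustrate. Late ascertainment weakens them further: surgery falls on Day 14 to 45, so several subjects may be dosed before a death is known, and a hold would protect fewer.

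A third reading goes the other way: that the plan also needs a numeric stopping threshold for repeated Grade 3 or 4 events or SAEs at 250 mg. The documents do not establish that. Any such threshold trades false holds against protection, and statisticians could reasonably differ on it. Intraductal subjects may also receive less than 500 mg before any cut, because duct volume limits the dose (5.1, 9.1), so a separate count at 250 mg is not clean.

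Finally, the remark in 13.3 about dosing being terminated for high AE sets no rule. It is compatible with the sponsor's discretionary powers and does not contradict 10.3.

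**Conclusion.** The point holds in limited form. The only mandatory response to a study-drug-related death that bears on dosing is the cut to 250 mg. No hold precedes the next subject, and at 250 mg there is no further prescribed step. This is a weakness in the safety rule itself, because the text as written moves on to dosing. It does not show a lack of authority to stop, a lack of case review, or a need for a particular event-rate threshold.

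The textual finding needs no event rate. Its size does: 0.03, 0.14 and 0.25 for a related death before the last of 30 subjects at assumed risks of 0.1%, 0.5% and 1%, with the low end the easiest to defend for a single dose at or below the labelled amount. The event is rare and grave, and the change costs little, so it should be made.

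One limit on the search: the sponsor's contact page within the SAE reporting part was not in the copy read. The table of contents lists it as contact information. A dosing hold stated there would change the conclusion.

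**What to change.** Add to Section 10.3, mirror it in 7.0, and cross-refer to 15.3:

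*After any study-drug-related death, at any dose, no further subject will receive fulvestrant until the medical monitor and the investigator have documented a decision to resume or to stop. The reduction to 250 mg applies only if dosing resumes.*

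Related can take the meaning already given in 11.2.4 (possible, probable or definite). Subjects already dosed continue follow-up and surgery as planned.

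The change uses the existing medical monitor and the existing 24-hour report, and needs no new committee. The downside is a possible short enrolment pause after a rare event. A re-trigger threshold for Grade 3 or 4 events or SAEs at 250 mg is optional and for the sponsor to decide.
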